	2. Subjects must have a histological diagnosis of locally advanced or metastatic malignant solid tumors. Subjects must have failed the established standard treatment, or the standard treatment does not exist; or subjects are intolerant of or have refused to receive standard treatment. All subjects must have received at least one previous line of systemic treatment. Subjects with known genomic alterations for which there are approved therapies (e.g., ALK mutated NSCLC, microsatellite instability high/mismatch repair deficient solid tumors, EGFR NSCLC, etc.,) will have received such therapies prior to the enrolling in this study.
	3. Subjects must have measurable or evaluable disease (according to RECIST 1.1, see Appendix 1);
	4. ECOG Performance Status ≤ 2 .
Inclusion Criteria	5. Life expectancy \geq 12 weeks.
	6. Subjects must have normal levels of total serum calcium and total phosphate.
	7. Subjects must have adequate organ and bone marrow function (subjects must not have received any hematopoietic growth factors, transfusion, or platelet within 1 week before the first dose).
	• CBC: neutrophils $\geq 1.5 \times 10^{9}$ /L, platelets $\geq 100 \times 10^{9}$ /L, hemoglobin ≥ 9.0 g/dL.
	• Liver function: total bilirubin $\leq 1.5 \times ULN$, unless known to have Gilbert's disease; ALT/AST $\leq 2.5 \times ULN$ without liver metastasis; ALT/AST $\leq 5 \times ULN$ with liver metastasis;
	• Coagulation: International normalized ratio (INR) $\leq 1.5 \times ULN$ and activated partial thromboplastin time (APTT) $\leq 1.5 \times ULN$ (for subjects undergoing anticoagulant therapy, the Investigator should ensure that both INR and APTT are within the safe and effective treatment range).

	 Renal function: serum creatinine ≤ 1.5 × ULN, or creatinine clearance ≥ 60 mL/min/1.73 m² in the condition of creatinine level > ULN; urine protein analysis ≤ 1 + (if ≥ 2+, 24 hours of urine protein test is required, if 24 hours urine protein <1 g, then allowed to enroll); Adequate cardiac function: left ventricular ejection fraction (LVEF) > 50% in two-dimensional echocardiography; 8. Subjects must have fully understood and voluntarily signed informed consent form (ICF) for this study.

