- 4. CBC with differential: whole blood count (absolute value) includes red blood cell count, white blood cell counts, and differential counts (neutrophils, lymphocytes, monocytes, eosinophils, and basophils), platelet count, hemoglobin, and hematocrit. This test should be completed within 7 days prior to the first dose. It is unnecessary to repeat on C0D1 if the subject has no clinical signs and indications. This test should be completed before dosing within 3 days prior to days C1D1, C1D8, C1D15, C1D28, C2D15, C2D28, CxD28, and safety follow-up period. An unscheduled exam can be performed if there are clinical indications.
- 5. Blood biochemistry includes ALT, AST, total bilirubin, BUN (urea nitrogen) or urea, Cr (creatinine), blood glucose, potassium, sodium, chlorine, calcium, phosphate, magnesium, total protein, albumin, albumin/globulin ratio, LDH (lactate dehydrogenase), and ALP (alkaline phosphatase). This test should be completed within 7 days prior to the first dose. It isn't required to repeat on C0D1 if the subject has no clinical signs and indications. This test should be completed before dosing within 3 days prior to days C1D1, C1D8, C1D15, C1D28, C2D15, C2D28, CxD28 and safety follow-up period. Among them, phosphate levels will also be used for PD analysis.
- 6. Coagulation functions include prothrombin time (PT), APTT, and INR. This test should be completed within 7 days prior to the first dose. It isn't required on C0D1 if the subject has no clinical signs and indications. This test should be completed before dosing within 3 days prior to C1D28, every 8 weeks (±7 days) in additional cycles, and safety follow up visit.

- 7. Urinalysis includes specific gravity, pH, white blood cells, red blood cells, proteins, glucose, ketones, and casts. This exam should be completed within 7 days prior to the first dose. If urine protein ++, it is recommended to test 24-hour urine protein quantitation as soon as possible (if within 72 hours). It isn't required on C0D1 if the subject has no clinical signs and indications. This test should be completed before dosing within 3 days prior to days C1D1, C1D8, C1D15, C1D28, C2D15, C2D28, CxD28, and safety follow-up period.

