4.5. Dose Limiting Toxicity (DLT) Definition

A DLT is defined as the occurrence of any of the following toxic reactions that are considered to be causally related to 3D185 by the PI within the first 35 days after the first dose.

- 1. Hematological toxicity:
 - 1. Grade 4 hematologic toxicity;
 - 2. Grade 3 febrile neutropenia (defined as ANC < $1,000/\text{mm}^3$, a single temperature of >

38.3 \mathbb{C} or a sustained temperature of \geq 38 °C for more than 1 hour) or Grade 3 neutropenia

lasts for more than 7 days with or without drug intervention;

3. Grade 3 thrombocytopenia with bleeding or require to platelet transfusion;

- 2. Non-hematologic toxicity:
 - 4. Any Grade ≥ 3 non-hematologic toxicity (except the following conditions that can be controlled by symptomatic treatment within 48 hours: nausea, diarrhea, vomiting, and electrolyte imbalance [except serum phosphorus]; Grade 3 fatigue with duration ≤ 7 days; Grade 3 hypertension that can be self-resolved or controlled by drugs to below 140/90 mmHg or baseline level within 72 hours);
 - 5. Serum phosphorus ≥7 mg/dL that is unable to recover to < 7 mg/dL within 14 days after phosphorus removal;
 - 6. With liver metastasis or baseline transaminase abnormalities: ALT/AST > 8 × ULN; without liver metastasis or baseline transaminase abnormalities: ALT/AST > 5 × ULN ;
 - 7. 3D185-related AEs that resulted in dose interruption of 3D185 for \geq 7 days in the first treatment cycle.

If the DLT is clinically recovered to Grade 0-1 within 28 days, the subject can resume the treatment of 3D185. If the subject can resume treatment, the Investigator may refer to the provisions of Section 6.3 (Precautions and Dose Modifications) for dose modifications to the same dose or reduce by one dose level.

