5.2. Inclusion Criteria

Subjects must meet all of the following criteria before they can be enrolled:

- 1. Age \geq 18 years.
- 2. Subjects must have a histological diagnosis of locally advanced or metastatic malignant solid tumors. Subjects must have failed the established standard treatment, or the standard treatment does not exist; or subjects are intolerant of or have refused to receive standard treatment. All subjects must have received at least one previous line of systemic treatment. Subjects with known genomic alterations for which there are approved therapies (e.g., ALK mutated NSCLC, microsatellite instability high/mismatch repair deficient solid tumors, EGFR NSCLC, etc.,) will have received such therapies prior to the enrolling in this study.
- 3. Subjects must have measurable or evaluable disease (according to RECIST 1.1, see Appendix 1);
- 4. ECOG Performance Status ≤ 2 .
- 5. Life expectancy ≥ 12 weeks.
- 6. Subjects must have normal levels of total serum calcium and total phosphate.
- 7. Subjects must have adequate organ and bone marrow function (subjects must not have received any hematopoietic growth factors, transfusion, or platelet within 1 week before the first dose).
 - CBC: neutrophils $\ge 1.5 \times 10^{9}$ /L, platelets $\ge 100 \times 10^{9}$ /L, hemoglobin ≥ 9.0 g/dL.
 - Liver function: total bilirubin $\leq 1.5 \times$ ULN, unless known to have Gilbert's disease; ALT/AST $\leq 2.5 \times$ ULN without liver metastasis; ALT/AST $\leq 5 \times$ ULN with liver metastasis;
 - Coagulation: $INR \le 1.5 \times ULN$ and $APTT \le 1.5 \times ULN$ (for subjects undergoing anticoagulant therapy, the Investigator should ensure that both INR and APTT are within the safe and effective treatment range).
 - Renal function: serum creatinine $\leq 1.5 \times \text{ULN}$, or creatinine clearance $\geq 60 \text{ mL/min}/1.73 \text{ m}^2$ in the condition of creatinine level > ULN; urine protein

analysis $\leq 1 + (\text{if } \geq 2+, 24 \text{ hours of urine protein test is required, if 24 hours urine protein <1 g, then allowed to enroll);$

- Adequate cardiac function: LVEF > 50% in two-dimensional echocardiography;
- 8. Subjects must have fully understood and voluntarily signed ICF for this study.

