7. EVALUATION INDICATORS AND EVALUATION CRITERIA

7.1. Screening Period

All subjects must sign ICF prior to the start of the study-related examination or operation. The study center should maintain the ICFs signed by the subjects, including those not enrolled.

During the screening period, complete prior medical history, demographic information, tumor history and prior tumor treatment history, vital signs, physical examination, and ECOG performance status should be recorded. The screening exams and evaluations should be performed within 28 days prior to the first dose. To avoid repeat exam, the results of clinical routine examination (such as echocardiography, virologic examination, tumor imaging evaluation) before informed consent are acceptable if within 28 days prior to the first dose. CBC with differential, serum chemistry, coagulation parameters, urinalysis, serum β -hCG test, 12-lead ECG, and ophthalmological examination should be performed within 7 days prior to the start of study treatment. The detailed screening examinations and evaluations can refer to Table 4 study flow chat.

Any prior medications taken within 28 days before the first dose must be recorded in the eCRF. The information includes generic name, administration and dosage, the reason for the treatment, dates of start and stop, whether to continue taking the medication during this trial, etc.

After the signing of the ICF and before starting dose, any SAEs associated with the protocol required procedures should be reported.

Baseline tumor assessment should be completed by imaging (CT, MRI) according to RECIST 1.1 within 28 days prior to enrollment.

The following screening procedures will be performed within 28 days (-28 to -1 days) before the first dose:

- Informed consent;
- Demographic information (including body weight and height)
- Medical history information,
- Tumor history and prior tumor treatment history;
- Inclusion/Exclusion criteria;
- Complete physical examination (perform within 7 days before the first dose);
- ECOG performance status (perform within 7 days before the first dose);

- Vital signs (perform within 7 days before the first dose);
- CBC with differential (perform within 7 days before the first dose);
- Serum chemistry (perform within 7 days before the first dose);
- Coagulation parameters (perform within 7 days before the first dose);
- Urinalysis (perform within 7 days before the first dose);
- 12-lead ECG (perform within 7 days before the first dose);

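### Criterion 7 counts the one-week ban on transfusion and growth factors back from the first dose, not from the qualifying blood count, so a subject can qualify on supported counts

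*Protocol*

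**What the plan says.** Criterion 7 sets limits for neutrophils (1.5 × 10⁹/L), platelets (100 × 10⁹/L) and hemoglobin ("hemoglobin ≥ 9.0 g/dL"). It qualifies them with a ban on supportive treatment: "subjects must not have received any hematopoietic growth factors, transfusion, or platelet within 1 week before the first dose". Section 5.2 repeats the ban with the same length and the same anchor ("received any hematopoietic growth factors, transfusion, or platelet within 1 week before the first dose").

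The timing of the count is set elsewhere. Note 4 to the flow chart (Table 3) says of the CBC: "This test should be completed within 7 days prior to the first dose". Section 7.1 agrees: "CBC with differential (perform within 7 days before the first dose". Note 4 adds: "It is unnecessary to repeat on C0D1 if the subject has no clinical signs and indications". The C0D1 procedures in Section 7.3.1 list no CBC. The next scheduled one is at C1D1, with a window of -3/+0 days (Section 7.3.2), after the single first dose and before daily dosing begins.

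The hematologic DLTs in Section 4.5 are stated as grades and events: Grade 4 hematologic toxicity, Grade 3 febrile neutropenia or prolonged Grade 3 neutropenia, and "Grade 3 thrombocytopenia with bleeding or require to platelet transfusion".

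**The concern.** The ban stands inside the marrow-function criterion, so its natural purpose is to ensure that the counts reflect the subject's own marrow. The count limits are applied at the blood draw, but the ban is measured from the first dose. The earlier the draw falls in its seven-day window, the less of the ban lies before it. With a draw on Day -7, nearly all of the ban falls after the count that it is meant to protect.

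Two consequences follow. A subject whose counts pass only because of recent support may be below the entry limits when 3D185 is first given. Such a subject also starts closer to the DLT thresholds, and the fall as support wears off would coincide with the start of study treatment. Section 8.4.2 does not treat a laboratory abnormality that is present at baseline and does not worsen as an adverse event. A deficit hidden by support at baseline can therefore surface later as a new event. Cohorts hold one subject at 25 mg and 50 mg and three thereafter, so a single event carries weight.

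**Working it through.** **Inputs.** Ban: one week before the first dose (synopsis; Section 5.2). CBC window: Day -7 to Day -1 (Table 3 note 4; Section 7.1). There is no Day 0, so Day -k is k days before C0D1. The protocol states no gap of its own between support and the draw, so there is no figure to reproduce.

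**Shortest permitted gap from support to the qualifying CBC.** The gap is the latest permitted support day minus the CBC day, both in days before the first dose. If the seventh day before dosing is itself barred (inclusive reading), the latest support is 8 days before and the gap is 8-k. If exactly seven days before is allowed (strict reading), the latest support is 7 days before and the gap is 7-k.

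| CBC day | Gap, inclusive (8-k) | Gap, strict (7-k) |
|---|---|---|
| Day -7 | 1 | 0 |
| Day -6 | 2 | 1 |
| Day -5 | 3 | 2 |
| Day -4 | 4 | 3 |
| Day -3 | 5 | 4 |
| Day -2 | 6 | 5 |
| Day -1 | 7 | 6 |

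Under either reading a count drawn the day after a transfusion is allowed: support on Day -8 and CBC on Day -7 (inclusive), or support on Day -7 and CBC on Day -6 (strict).

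**When the next count falls.** C0D1 is followed by a 7-day washout, so C1D1 is study Day 8 and its -3/+0 window covers Days 5 to 8. Without clinical signs, no count is required between the qualifying draw and the first dose.

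**What one misattributed DLT does.** Appendix 7 works from x/n and (x-1)/n against the equivalence interval (16%, 30%):

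- 0/3 = 0% is below the interval: escalate. With one more event, 1/3 = 33.3% is above it and (1-1)/3 = 0% is below it: stay.
- 1/3: stay. With one more event, 2/3 = 66.7% is above and 1/3 = 33.3% is not below: de-escalate.
- 1/6 = 16.7% is inside: stay. With one more event, 2/6 = 33.3% is above and 1/6 = 16.7% is not below: de-escalate.

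In the accelerated phase the trigger is lower. One Grade 2 or higher drug-related event at 25 mg or 50 mg adds two subjects and starts the i3+3 phase at that dose. The maximum for that phase is then 42 or 36 instead of 30 (Section 4.1).

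**After re-anchoring, with the one-week length kept for illustration.** Inclusive: the gap is at least 8 days for every permitted CBC day, and the latest permitted support falls k+8 days before the first dose, from 9 days (CBC on Day -1) to 15 days (CBC on Day -7). Strict: the gap is at least 7 days, and the latest support falls 8 to 14 days before.

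**The case against.** The day count is not in dispute; the objection is to the consequence, and much of it stands.

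- A reader might infer that the supported count becomes the baseline for the hematologic DLTs. Section 4.5 does not support this. Those DLTs are absolute grades and events. Where the protocol wants a baseline-dependent rule, as for transaminases and hypertension, it says so. A fall from a supported count is not a DLT unless it reaches those limits.
- A reader might infer that a false DLT follows automatically. A DLT must be judged causally related to 3D185. Section 8.5.2 requires alternative causes to be considered, and medication from 28 days before the first dose is recorded, so recent support should be visible. The filter is only partial, because events classed as of uncertain causality count as drug-related.
- A reader might infer that the CBC is never repeated. Note 4 makes a C0D1 repeat unnecessary only without clinical signs, and it permits unscheduled tests. The C1D1 count could also show a fall before daily dosing begins.
- Other entry rules narrow the group: washout of anti-tumor therapy (generally 4 weeks, with 6-week and 2-week exceptions), recovery of earlier treatment toxicity to Grade 0-1, and investigator discretion (exclusions 2, 5 and 19). None sets an interval between support and the draw, and a supported count can mask incomplete recovery.
- The i3+3 output is a recommendation that the SMC weighs with all safety data, and the MTD is selected by isotonic regression across all doses (Sections 4.1 and 4.2). Section 6.3.1 does not list myelosuppression among the expected toxicities.

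Finally, the protocol never states that a full support-free week before the CBC was intended. The two windows do not contradict each other; they share an anchor that leaves a gap.

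**Conclusion.** The gap is real and follows from the text alone: a subject can meet criterion 7 exactly as written on counts drawn one day after support. The guaranteed support-free interval before the draw is 1 to 7 days, or 0 to 6 on the strict reading, depending on the CBC day. These are worst-case minimum intervals, not typical ones.

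The possible harm is a subject who starts below the entry limits and nearer the absolute DLT thresholds, with some chance that a later fall is attributed to 3D185. For that to alter dose finding, the event must reach a DLT grade (or Grade 2 in the accelerated phase), be judged related, and not be discounted by the SMC. The protocol gives no rate of transfusion or growth-factor use and no duration of their effect, so the frequency cannot be estimated; it is probably low. The documents do not support a claim that the DLT data or the MTD would be materially biased. The point is worth correcting because small cohorts make each event count and because the correction is cheap.

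**What to change.** Reconcile the anchor of the ban in criterion 7 (synopsis and Section 5.2) with the CBC window (Table 3 note 4 and Section 7.1). Count the sponsor's support-free interval back from the blood draw used to qualify the subject, and continue it until the first dose. State also whether the boundary day is included. The length of the interval is a clinical decision for the sponsor; if the present week is kept, the ban reaches further back from dosing, as shown in the working.

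The cost is one phrase in two places and no new procedure. A few recently supported subjects would be sampled or dosed slightly later within the 28-day screening period. For example, support on Day -8 would move the draw to Day -1 on the strict reading. On the inclusive reading, the first dose would move by at least a day.

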1. LIST OF ABBREVIATIONS AND DEFINITIONS OF TERMS

Abbreviations and Terminology	Definition	
AE	Adverse Events	
ALT	Alanine Aminotransferase	
ANC	Absolute Neutrophil Count	
APTT	Activated Partial Thromboplastin Time	
AST	Aspartate Aminotransferase	
AUC	Area Under Curve	
BUN	Blood Urea Nitrogen	
CI	Confidence Interval	
CL	Clearance	
CR	Compete Response	
CRF	Case Report Form	
CSR	Clinical Study Report	
СТ	Computed Tomography	
CTCAE	Common Terminology Criteria for Adverse Events	
СҮР	Cytochrome P450	
DCR	Disease control rate	
DLT	Dose Limiting Toxicity	
DOR	Duration of response	
EC	Ethics Committee	
ECG	Electrocardiogram	
ECOG	Eastern Cooperative Oncology Group	
eCRF	Electronic Case Report Form	
EDC	Electronic Data Capture	

FAS	Full Analysis Set		
FDG-PET	Fluorodeoxyglucose - Positron Emission Tomography		
FGF	Full analysis set		
FGFR	Fibroblast Growth Factor Receptors		
GCP	Good Clinical Practice		
HBV	Hepatitis B Virus		
HCV	Hepatitis C Virus		
IB	Investigator's Brochure		
IC50	The half maximal inhibitory concentration		
ICF	Informed Consent Form		
IEC/IRB	Institutional Review Board /Independent Ethics Committee		
INR	International Normalized Ratio		
LDH	Lactic Acid Dehydrogenase		
LDL	Low density lipoprotein		
LVEF	Left Ventricular Ejection Fraction		
MedDRA	Medical Dictionary for Regulatory Activities		
MRI	Magnetic Resonance Imaging		
NCI	National Cancer Institute		
NE	Not Evaluated		
NTL	Non-Target Lesions		
NYHA	New York Heart Association		
ORR	Objective Response Rate		
OS	Overall Survival		
PD	Progressive Disease		
PFS	Progression-free survival		

РК	Pharmacokinetics
PR	Partial Response
PT	Prothrombin Time
QD	Once Daily
QTc	QT Interval
RECIST	Response Evaluation Criteria in Solid Tumors
RD	Recommanded Dose
SAE	Serious Adverse Event
SD	Stable Disease
SMC	Safety Monitoring Committee
TL	Target Lesions
T _{max}	Time of Maximum Concentration Observed
ULN	upper limit of normal
V _{ss}	Volume of Distribution at Steady State
WBC	White Blood Cell

2. STUDY BACKGROUND

2.1. Disease Background

Cancer is a significant public health problem worldwide. It is the second leading cause of death in the United States (US). The American Cancer Society (ACS) estimates that 1,762,450 new cancer cases and 606,880 cancer deaths will occur in 2019 in the US^[2]. The top five most common tumors in the US are breast cancer, lung cancer, prostate cancer, colorectal cancer, and melanoma^[2]. China has a significant cancer burden in the world. According to the latest data from the National Central Cancer Registry of China, it was estimated that there were about 4,292,000 new cancer cases and 2,814,000 cancer deaths in China in 2015. More importantly, the cancer profile in China is markedly different from those of developed countries. The four most common cancers diagnosed in China were lung, stomach, liver, and esophageal cancer. These cancers account for 57% of cancers diagnosed in China, compared with 18% in the United States^[3]. Also, these cancers diagnosed in China account for between 1/3 and 1/2 of the global incidence burden^[3]. At present, diagnosis of cancers at an early stage is uncommon in China, and majority of cancer were diagnosed at locally advanced or advanced stage. which is one of the reasons for the generally low cancer survival rate in China^[4-6]. Globally, advanced cancers are generally insensitive to chemotherapy and associated with poor prognosis.

FGFRs are members of the receptor tyrosine kinases (RTKs) superfamily^[7-9]. Evolutionarily, FGFRs are relatively conserved, with high homology among subtypes. Fibroblast growth factors (FGFs) act as ligands, have high-affinities for FGFRs and can regulate a wide range of physiologic processes, including embryonic development, organ differentiation, angiogenesis, cell proliferation, migration, and survival, etc., by the transduction of multiple levels signaling pathway^[7-9]. More and more evidence indicates that FGFR/FGF pathway abnormalities have a close relationship with many malignant tumors^[7-9].

Aberrations in FGFR are widespread in the development of various tumors. There are three major forms of FGFR aberrations including: 1) gene fusion; 2) activation mutation; 3) gene amplification/protein overexpression^[7-9]. Aberrant FGFR signaling contributes to carcinogenesis by serving as "driver mutations," where the acquisition of somatic molecular alterations directly stimulates cancer cell proliferation and survival; or driving neoangiogenesis; or resulting in resistance to anticancer agents^[9].

2.1.1.FGFR gene fusions

FGFR gene fusions occur in several malignancies, such as glioblastoma, bladder cancer, non-small cell lung cancer, and cholangiocarcinoma, etc. Fusions have been described in the FGFR1-3 genes with multiple partners, including TACC1, TACC3, BAIAP2L1, BICC1, and AHCYL1. Among them, fusions involving FGFR3 and TACC3 are found in 3% to 7% of glioblastomas and 3% to 6% of urothelial bladder carcinomas^[9]. In vivo, both FGFR3–TACC3–initiated bladder carcinoma and glioblastoma were sensitive to specific FGFR inhibitors, suggesting oncogenic addiction to the FGFR gene fusion.

